8.3.2. Discontinuation of Investigational Product

Patients will be discontinued from study drug if they are confirmed to have the following Exclusion Criteria:

- [7] to [9]—T1DM (the patient will also be discontinued from the trial)
- [11] to [12]—safety concerns, for example, patients will be discontinued from study drug if they develop confirmed pancreatitis (if not confirmed, study drug may be restarted) (see Section 10.4.1.2.2).
- [18]—unable to assess primary endpoint (the patient will also be discontinued from the trial)
- [19] to [21]—pregnancy or breastfeeding (the patient will also be discontinued from the trial)
- [29] to [33]—potential bias.

The patient should be discontinued from study drug for abnormal liver tests when the patient meets 1 of the following conditions (and after consultation with the Lilly CRP or designee):

- Alanine aminotransferase (ALT) or aspartate aminotransferase (AST) $>6 \times$ upper limit of normal (ULN)
- ALT or AST $>5 \times$ ULN for more than 2 weeks
- ALT or AST $>3 \times$ ULN and total bilirubin level $>2 \times$ ULN or prothrombin time $>1.5 \times$ ULN
- ALT or AST $>3 \times$ ULN with the appearance of fatigue, nausea, vomiting, right upper-quadrant pain or tenderness, fever, rash, and/or eosinophilia ($>5\%$).
- Alkaline phosphatase (ALP) $>3 \times$ ULN
- ALP $>2.5 \times$ ULN and total bilirubin $>2 \times$ ULN
- ALP $>2.5 \times$ ULN with the appearance of fatigue, nausea, vomiting, right upper-quadrant pain or tenderness, fever, rash, and/or eosinophilia ($>5\%$)

The most common AEs experienced by patients receiving dulaglutide are gastrointestinal symptoms known to be associated with GLP-1 RA therapy. These symptoms may be self-limited. Patients judged by the investigator unable to tolerate study drug (e.g., intractable nausea, vomiting and diarrhea) should temporarily (or permanently) discontinue study drug, but remain in the study.

Patients unable to tolerate the study drug after a potential dosage change at Week 4 may temporarily go back to the previously assigned study drug. However, they should be encouraged to take their assigned study drug, if possible.

Study drug should be temporarily discontinued in any individual suspected of having a severe or serious allergic reaction to study drug or other serious safety concerns. Study drug may be restarted when/if it is safe to do so, in the opinion of the investigator.

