5.15.8. Analysis of Laboratory Analytes

All laboratory measurements (including scheduled and unscheduled) will be listed using all randomized population. A listing of patients with treatment-emergent abnormal laboratory, with the normal ranges and potentially clinically relevant reference limits for all laboratory tests, with serum calcitonin levels suggestive of thyroid C-cell abnormalities, will be listed separately. For certain labs, age-dependent reference ranges will be used as appropriate.

Descriptive summary statistics will be presented for sodium, potassium, calcium, and glucose random at each scheduled visit in raw data and change from baseline without formal statistical analysis.

For each continuous laboratory measurement listed below, the change from baseline will be summarized for each treatment. The summary statistics include number of patients, mean, SD, minimum, Q1, median, Q3, and maximum. These analytes will be analyzed using ANOVA on the ranks, with treatment as a fixed effect. LOCF will be used to impute missing postbaseline values. Wilcoxon signed-rank test will be used to compare baseline and each post-baseline visit within the same treatment:

- Pancreatic enzymes (lipase, amylase, P-amylase)
- Liver test panel (ALT, AST, CK, alkaline phosphatase, total bilirubin, direct bilirubin, albumin)
- Renal (eGFR, albumin-to-creatinine ratio [ACR], serum creatinine, serum BUN, serum cystatin C, uric acid)
- Serum lipids (total cholesterol, HDL cholesterol, LDL cholesterol, triglycerides)
- Hormone-related safety assessed by the effect on serum
 - Prolactin
 - Insulin-like growth factor-1

- Testosterone (males only)
- Cortisol
- Estradiol
- Luteinizing hormone
- Calcitonin
- hematology (hemoglobin, hematocrit, RBC, mean cell volume, mean cell hemoglobin concentration, WBC, neutrophils [segmented], lymphocytes, monocytes, eosinophils, basophils, platelets)

The above lab measures will also be compared to reference range to determine whether they are abnormally high, low, or normal. The incidence and percent of high, low, and normal values will be summarized for each of the treatment arms and compared using the Fisher's exact test.

Shift tables of the change from maximum baseline to maximum postbaseline, from baseline to Week 26, and from baseline to Week 52 in the selected analytes using clinical meaningful thresholds will be summarized separately. The selected analytes include creatinine, ALT, AST, ACR, and calcitonin.

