Similar analysis will be performed on the change from minimum baseline to minimum postbaseline, and the change from baseline to Week 26, and from baseline to Week 52 in eGFR, creatinine, ALT, AST, ACR, and calcitonin to that for the change from maximum baseline to maximum postbaseline.

Summary of pancreatic enzymes (p-amylase, amylase, lipase) by threshold ($>1\times$ upper limit of normal [ULN], $\geq 3\times$ ULN) from screening to Week 52 will be summarized descriptively using all ITT population, ITT population with normal range baseline, ITT population with $>1\times$ ULN baseline.

The number of patients and percentage of patients with a serum calcitonin ≥ 35 pg/mL and a simultaneous increase of 50% from baseline, and patients with a serum calcitonin ≥ 20 pg/mL and <35 pg/mL with a simultaneous increase 50% from baseline to Week 52 will be summarized using Fisher's exact test.

A summary of the number of patients and percentage of patients exceeding $2\times$, $3\times$, $5\times$, and $8\times$ ULN for each treatment at baseline, Week 26, and Week 52 will be presented for ALT, AST, and total bilirubin using Fisher's exact test.

A summary of the number of patients and percentage of patients meeting notable criteria for potential hepatotoxicity (ALT or AST $>3\times$ ULN and total bilirubin $>2\times$ ULN) for each treatment group at each postdose visit will be presented.

The number of patients and percentages for patients with pancreatic enzymes above ULN and greater than or equal to $3\times$ ULN will be summarized at baseline and by visit for each treatment group.

Number of patients and percentage for female patients showing positive outcome from serum pregnancy test will be summarized descriptively for each treatment group from baseline to Week 26, from Week 26 to Week 52, and from baseline to Week 52.

Number of patients and percentage of subjects of normal and abnormal values for each urinalysis test: protein, glucose, ketones, blood, and leukocyte esterase will be presented descriptively for each treatment group from baseline to Week 26 and from baseline to Week 52.

Additional analyses may be conducted if deemed necessary.

5.15.9. *Pubertal Progression Evaluation*

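### The ALT, AST and total bilirubin ULN-multiple table counts fixed visits only, so it omits peaks at Week 13 or on unscheduled samples that resolve before Week 26 or Week 52; the gap is widest for isolated bilirubin.

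*SAP*

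**What the plan says.** SAP 5.15.8 plans numbers and percentages of patients above 2, 3, 5 and 8 times ULN, compared by Fisher's exact test. The analytes and time points are fixed by the words "for each treatment at baseline, Week 26, and Week 52 will be presented for ALT, AST, and total bilirubin".

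The same section plans other outputs that bear on liver tests:

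- "Shift tables of the change from maximum baseline to maximum postbaseline", using clinically meaningful thresholds that are not given as numbers. On coverage: "The selected analytes include creatinine, ALT, AST, ACR, and calcitonin".
- The combined hepatotoxicity criterion (ALT or AST above 3 times ULN with total bilirubin above 2 times ULN), with counts "for each treatment group at each postdose visit will be presented".
- A comparison with the reference range for the liver panel, which includes total bilirubin: "The incidence and percent of high, low, and normal values will be summarized for each of the treatment arms", with Fisher's exact test.
- Listings: "All laboratory measurements (including scheduled and unscheduled) will be listed using all randomized population". Patients with treatment-emergent abnormal values are listed separately.

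In the protocol, Attachment 1 places the chemistry panel at Week 13 as well as at baseline and Week 26. Section 10.4.3 says the investigator should start clinical and laboratory monitoring after specified liver elevations. Section 8.3.2 states: "The patient should be discontinued from study drug for abnormal liver tests when the patient meets 1 of the following conditions". Patients who stop study drug permanently keep attending scheduled visits.

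**The concern.** A table of ULN multiples is meant to show how many patients ever reached a given degree of elevation. A snapshot at Week 26 or Week 52 shows how many were elevated on that day. The two differ whenever an elevation comes and goes between visits. Some elevations will have led to study drug being stopped, and because those patients stay in the study, their Week 26 or Week 52 sample may be taken off drug.

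SAP 5.15.8 uses interval wording where it means an interval. Pancreatic enzyme thresholds run from screening to Week 52, and urinalysis runs from baseline to each of the two endpoints. Pancreatic enzymes also get a by-visit table, so they have both kinds of summary. The liver multiples have only the visit form, and a programmer would build the table that way.

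At stake is the between-arm count of ALT, AST and bilirubin elevations by degree. The primary endpoint and the multiplicity-controlled tests do not depend on it.

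**Working it through.** The plan gives no figure to reproduce, so the check is one of coverage.

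**Step 1. Planned outputs side by side (all SAP 5.15.8).**

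| Output | Total bilirubin included? | Time basis | Stated ULN multiples | Between-arm test stated |
|---|---|---|---|---|
| ULN-multiple table | Yes | Baseline, Week 26, Week 52 | 2, 3, 5, 8 | Fisher |
| Maximum-postbaseline shift tables | Not named (ALT and AST are) | Maximum over post-baseline; unscheduled samples not mentioned | None given | None |
| Combined criterion | Only jointly with ALT/AST | Each post-dose visit; unscheduled samples not mentioned | ALT/AST >3 with bilirubin >2 | None |
| High/low/normal incidence | Yes | Not stated | None (reference range only) | Fisher |
| Listings | Yes | All samples, including unscheduled | Not a count | None |

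The rule "LOCF will be used to impute missing postbaseline values" is written for the continuous change-from-baseline analyses. Even if it were applied to the threshold table, it would fill missing values only. It would not replace an observed normal value at Week 26 with a Week 13 peak.

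**Step 2. Trace two patients.**

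*Patient A* has ALT above 6 times ULN at Week 13, stops study drug, and is back within range at Weeks 26 and 52. In the ULN-multiple table this patient is counted in no post-baseline row. By maximum post-baseline value the same patient would be counted in the 2, 3 and 5 times rows (and in the 8 times row only if the peak exceeded 8). The peak should appear in the ALT shift table, but against thresholds not stated as numbers and without a stated test.

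*Patient B* has total bilirubin above 2 times ULN at Week 13 with unremarkable ALT and AST, and is normal at Weeks 26 and 52. The ULN-multiple table does not count this patient. Bilirubin is not named for the shift tables, and the combined criterion is not met. The high/low/normal table may show one high value, depending on its unstated window. The value appears in the listings. No planned output counts it by ULN multiple.

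**Step 3. Illustration of how a snapshot loses short elevations.** Assume an elevation lasts D weeks (D at most 13) and starts at a uniformly random time in Weeks 0 to 26. It is present at Week 26 with probability D/26, and at Week 13 or Week 26 with probability 2D/26.

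| D (assumed) | Week 26 only, D/26 | Week 13 or 26, 2D/26 | At neither visit, 1 − 2D/26 |
|---|---|---|---|
| 4 weeks | 4/26 = 15% | 8/26 = 31% | 69% |
| 8 weeks | 8/26 = 31% | 16/26 = 62% | 38% |
| 13 weeks | 13/26 = 50% | 26/26 = 100% | 0% |

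Neither the durations nor the uniform onset come from the documents.

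**The case against.** The strongest reply is that the plan as a whole does not lose these peaks. ALT and AST maxima go into shift tables. The combined criterion, which the SAP itself singles out as notable, is tabulated at every post-dose visit and so includes Week 13. The liver panel has a Fisher comparison against the reference range, and all values are listed. SAP 5.5 summarises discontinuations from study medication by arm, SAP 5.9 lists patients with study drug changes, and Protocol 10.4.1 requires the circumstances of an AE-related stop to be reported. This stands. A reader might infer that peaks leading to a stop go unreported; the documents do not support that.

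A reader might also infer that the stopping rule makes elevations transient and so biases the whole table towards no signal. Protocol 8.3.2 does not support this. For ALT and AST, stopping needs more than 6 times ULN, more than 5 times for over 2 weeks, or more than 3 times with a further finding (bilirubin, prothrombin time, symptoms or eosinophilia). Isolated ALT or AST between 2 and 5 times ULN without such findings triggers no stop. Isolated bilirubin triggers none at any level.

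Nor are repeat samples strictly required after an elevation: Protocol 10.4.3 says monitoring should be started, and Attachment 3 says selected tests may be obtained.

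Finally, much of the loss in the illustration comes from the sampling schedule. With D of 4 weeks, 69% of elevations are present at neither Week 13 nor Week 26. Changing the table recovers those only where an unscheduled sample was taken.

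What the reply leaves open is narrower. The only table with stated ULN multiples for each analyte and a between-arm test remains a snapshot, and isolated bilirubin has no substitute.

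**Conclusion.** The point holds for this table, at low severity. As written, the ULN-multiple counts and their Fisher tests omit Week 13 and unscheduled peaks that have resolved by Week 26 or Week 52, including ALT or AST values that led to stopping study drug.

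For ALT and AST, the loss is a count by stated multiple with a between-arm test, since the peaks themselves should be visible in the shift tables. For joint elevations, the open question is whether unscheduled samples enter the per-visit summary. For isolated total bilirubin at Week 13 or on an unscheduled sample, no ULN-multiple count is planned at all.

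The size in patients cannot be derived. The percentages in the illustration rest on assumed durations and onset, and should not be read as an estimate of missed cases. The verdict assumes that the SAP's time points are programmed literally.

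**What to change.** Amend SAP 5.15.8 to say, in substance: for ALT, AST and total bilirubin, each patient is counted once by the maximum post-baseline value, using scheduled and unscheduled samples, over baseline to Week 26 and over baseline to Week 52, at 2, 3, 5 and 8 times ULN. Apply the combined hepatotoxicity criterion to all post-baseline samples on the same basis. Keep the by-visit table as supplementary.

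It would help to state the shift-table thresholds as numbers at the same time, and to say whether their post-baseline maximum includes unscheduled samples.

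The cost is one SAP sentence and a small change in programming. The SAP already plans to list every scheduled and unscheduled laboratory value, so no extra data collection, visits or patients are needed, and no primary or key secondary analysis changes.

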10.4.2.3. Assessment of Pubertal Progression

Patients’ pubertal progression will be assessed throughout the trial. Tanner staging will be performed at baseline, 26 weeks and 52 weeks: those patients who have reached Tanner stage 5 will not be evaluated again. Morning hormone levels (estradiol, testosterone in males, LH, IGF-1, cortisol, and prolactin) will be performed at baseline, 26 weeks, and 52 weeks.

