Attachment 4. Definitions of Highly Effective and Effective Contraception

Participants of childbearing age who are sexually active should be counseled to use either 1 highly effective method of contraception or 2 effective methods of contraception combined for the duration of the trial and for 30 days after (until Visit 801). Childbearing potential is usually considered from menarche to menopause. Menarche should be considered if the female participant is close to the average age for menarche in her country or shows signs of puberty beyond Tanner stage 1. Any past bleeding or spotting, no matter how little, should be considered a potential menarche.

1. Highly effective methods of contraception (use 1 form)
 - a. Combined oral contraceptive pill and mini-pill
 - b. NuvaRing®
 - c. Implantable contraceptives
 - d. Injectable contraceptives (such as Depo-Provera®)
 - e. Intrauterine device (such as Mirena® and ParaGard®)
 - f. Contraceptive patch – ONLY women <198 pounds or 90 kg
 - g. Total abstinence¹
 - h. Vasectomy – for men in clinical trials
2. Effective methods of contraception (use 2 forms combined)
 - a. Male condom with spermicide
 - b. Female condom with spermicide
 - c. Diaphragm with spermicide
 - d. Cervical sponge
 - e. Cervical cap with spermicide

For patients using oral contraceptive pills, if vomiting occurs, advise the patient to use a supplemental barrier method of contraception.

Females who have undergone or who have the following will not be considered of childbearing potential:

- a. Female sterilization
- b. Hysterectomy
- c. Mullerian agenesis (Mayer-Rokitansky-Küster-Hauser syndrome [also referred to as congenital absence of the uterus and vagina])

¹Total abstinence is defined as refraining from heterosexual intercourse during the entire period of risk associated with the study treatments. The reliability of sexual abstinence needs to be evaluated in relation to the duration of the clinical trial and the preferred and usual lifestyle of the subject (CTFG 2014).

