4.3. Exploratory Objectives

The exploratory objectives are to compare the dulaglutide 0.75 mg and dulaglutide 1.5 mg arms (individually and pooled) to placebo with respect to the following parameters at 26 weeks, and to assess the following parameters in the dulaglutide 0.75 mg and dulaglutide 1.5 mg arms (individually and pooled) at Week 52 (unless otherwise specified):

- Percentage of patients with HbA1c $\leq 6.5\%$ at Weeks 26 and 52
- Change in HbA1c between baseline and Week 13
- Percentage of patients having HbA1c $\leq 6.5\%$ without severe, documented symptomatic (<70 mg/dL), or probable hypoglycemic episodes at Weeks 26 and 52
- Percentage of patients having HbA1c $< 7.0\%$ without severe, documented symptomatic (<70 mg/dL), or probable hypoglycemic episodes at Weeks 26 and 52
- Change in weight between baseline and Weeks 26 and 52
- Change in hormone-related safety assessed by the effect on morning serum prolactin, insulin-like growth factor-1 (IGF-1), estradiol, testosterone (males only), luteinizing hormone (LH), and cortisol between baseline and Weeks 26 and 52
- Change in serum lipids between baseline and Weeks 26 and 52
- Change in Tanner staging between baseline and Weeks 26 and 52
- Change in BMI standard deviation score (SDS) between baseline and Weeks 26 and 52
- Change in height and height SDS between baseline and Weeks 26 and 52
- Change in waist circumference between baseline and Weeks 26 and 52
- Change in the EQ-5D-Youth version (EQ-5D-Y) visual analogue scale (VAS) score between baseline and Weeks 26 and 52
- Percentage of patients reporting each level of problem on each dimension of the EQ-5D-Y at baseline and Weeks 26 and 52
- Assess effect of dulaglutide on measures of insulin resistance, beta cell function, and serum adiponectin at Weeks 13 and 26

- Change in basal insulin dose from baseline to Week 26 and from baseline to Week 52

5. A Priori Statistical Methods

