A shift table will be presented in those pubertal patients at baseline (Visit 2) to evaluate the change in Tanner Staging from baseline to Week 26, and baseline to Week 52 separately for male and female group at each treatment group without pooling. This includes no change and an increase in 1, 2, 3, and 4 levels. The likelihood ratio p-value will be the test statistic.

Morning serum hormone (estradiol, testosterone, LH, IGF-1, cortisol, and prolactin) will be analyzed with the method described in Section 5.15.8.

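### The only test of Tanner-stage change is an undefined likelihood-ratio p-value split by sex and arm, which gives no contrast of pooled or single-dose dulaglutide with placebo

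*SAP*

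**What the plan says.** SAP 4.3 (and Protocol 6.3) sets exploratory objectives to "compare the dulaglutide 0.75 mg and dulaglutide 1.5 mg arms (individually and pooled) to placebo" at Week 26, and to assess the dulaglutide arms at Week 52. One listed item is "Change in Tanner staging between baseline and Weeks 26 and 52".

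SAP 5.15.9 is the only place that gives a test for this item. It plans a shift table for patients who are pubertal at baseline, from baseline to Week 26 and to Week 52, "separately for male and female group at each treatment group without pooling". The content is described as change categories: "This includes no change and an increase in 1, 2, 3, and 4 levels". The test is given in one sentence: "The likelihood ratio p-value will be the test statistic". No null hypothesis, table layout or arm contrast is named, and a p-value is not itself a test statistic.

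Three other provisions bear on this:

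- SAP 5.2 sets a default for categorical variables, Fisher's exact test across the three arms and for All Dula against placebo, but allows exceptions. It also rules out inference among treatment groups after Week 26.
- Protocol 10.4.2.3 schedules staging at baseline, Week 26 and Week 52, but "those patients who have reached Tanner stage 5 will not be evaluated again".
- SAP 5.6 compares baseline Tanner stage between arms. That is a comparability check, not a test of change.

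**The concern.** The objective asks for three contrasts at Week 26: pooled doses, 0.75 mg and 1.5 mg, each against placebo. SAP 5.2 counts the pooled doses as one of the treatment groups, so the instruction not to pool most naturally removes that group from this analysis. The test sentence supplies no single-dose contrast either. A programmer following 5.15.9 would have to guess the table, and no guess consistent with the text returns what SAP 4.3 asks for.

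Pubertal progression is a natural safety question for a drug given to patients aged 10 to under 18. If the test is weak, a real slowing or speeding of puberty may be missed. If it is run twice without correction, chance findings become more likely. If it is applied to the wrong table, its p-value does not concern treatment at all.

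**Working it through.** **Sample size.** The documents give no power, effect or stage distribution for Tanner change. The stated power is for HbA1c and fixes 40 completers per arm (120/3). It reproduces with a difference of 0.65 and SD 1:

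- Pooled v placebo: SE = √(1/80 + 1/40) = 0.194; 0.65/0.194 − 1.96 ≈ 1.40; power 91.9% (stated: at least 90%).
- Single dose v placebo: SE = √(2/40) = 0.224; 0.65/0.224 − 1.96 ≈ 0.95; power 82.8% (stated: at least 80%).

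**Assumptions for the Tanner simulation (not in the documents).** 26 girls and 14 boys per arm, so all 40 completers are informative, which is a best case. Change of 0/+1/+2 stages: placebo 55/35/10%, both doses 80/17/3%. Two-sided 5% level, asymptotic p-values.

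**Between-arm reading.** The planned test is a likelihood-ratio chi-square on arm by change category, three arms, within each sex. The alternative is a sex-stratified ordinal test of pooled doses v placebo.

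| Scenario | Girls | Boys | Either sex | Stratified ordinal, pooled v placebo |
|---|---|---|---|---|
| 26/14 per arm | 47% | 27% | 61% | 82% |
| 20/20 per arm | 37% | 36% | 59% | 81% |
| 13/7 per arm (half informative) | – | – | about 39% | 54% |
| 26/14, small effect (65/30/5 v 75/22/3) | – | – | 18% | 22% |

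Check on the either-sex figure: 1 − (1 − 0.47)(1 − 0.27) = 0.61.

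**Where the gap comes from (26/14 per arm).**

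- Respecting order on the SAP's own table (three arms, one sex) gives 52% in girls and 30% in boys, a gain of about 3 to 6 points.
- Stratifying by sex and pooling doses without using order already gives about 75%. Order then adds about 6 points.
- Over other assumed distributions, with 3 or 4 filled categories and 10 to 25 patients per arm per sex, ignoring order costs 2 to 12 points at the nominal level.

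If pubertal means beyond stage 1, as the contraception attachment's phrase "shows signs of puberty beyond Tanner stage 1" suggests, the largest possible rise is from stage 2 to stage 5. The +4 category then cannot occur, and at most four categories can be filled.

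**False positives.** Two independent tests at 5% give 1 − 0.95² = 9.75% for either sex. In these sparse tables the likelihood-ratio test itself runs at about 6% to 7%: 1 − 0.94² = 11.6% and 1 − 0.93² = 13.5%. The simulated value is 13%, against 4.8% for the single stratified ordinal test.

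**Within-arm reading.** If the p-value were attached to baseline stage by later stage inside one arm, its null would be that the two stages are independent. Stage persists or advances, so this is false with or without drug. With baseline stages 2/3/4 at 25/35/40% and change 65/30/5%, p<0.05 occurs in about 68%, 93%, 99.5% and 100% of simulated arms of 10, 14, 20 and 26 patients.

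**The case against.** **The intent is guessable.** The change categories in 5.15.9 and the comparisons in SAP 5.2 point to a between-arm test. This stands. A reader might infer that the plan commits to the within-arm test and its almost certain significance. The text does not support that: the within-arm reading is an ambiguity to close, not the likely plan.

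**Order is a small part of the loss.** This stands. A reader might blame the gap of about 20 points on ignoring stage order. The decomposition shows otherwise: most of it comes from splitting by sex and not pooling doses.

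**The power figures use too many patients.** This stands in part. Patients at stage 1 or stage 5 at baseline contribute nothing to the comparison, and 26 + 14 uses every planned completer. One cannot say that the ordinal test would usually find an effect: with half the patients it has 54%, and with a small effect 22%. It is still ahead in each scenario, though only by 4 points in the last.

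**Fisher's test.** A reader might see a breach of a rule to use Fisher's exact test only. That wording is in the revision history. The current default in SAP 5.2 allows exceptions, and 5.15.9 makes one. For the same reason the default cannot be relied on to supply the missing pooled contrast.

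**Importance.** Tanner change is exploratory and has no part in the multiplicity scheme. Height, height SDS and six serum hormones also bear on growth and puberty. Separate display by sex is sensible. All of this stands and limits the severity, but does not supply the contrasts that the objective names.

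**Conclusion.** The point holds. SAP 5.15.9 leaves its one test of Tanner change undefined and, as written, returns neither the pooled-dose nor the single-dose contrasts with placebo that SAP 4.3 asks for at Week 26.

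On the likely reading, the planned pair of tests trails one stratified ordinal test by about 21 points of power in the main scenario (61% v 82%), 15 with half the informative patients (39% v 54%) and 4 with a small effect (18% v 22%). Its either-sex false-positive rate is about 10% to 13% against about 5%. The stage distributions, sex split and effects are assumptions, so these are illustrations of size, not forecasts.

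The p-value is also not limited to Week 26, which sits badly with the bar in SAP 5.2 on later inference between groups. The primary and key secondary results are untouched. Severity is low to moderate.

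**What to change.** In SAP 5.15.9, replace the likelihood-ratio sentence with one between-arm ordinal test of stage change at Week 26, stratified by sex: van Elteren, or the CMH row-mean-score test, with exact p-values. Apply it to pooled dulaglutide v placebo and to each dose v placebo. The single-dose contrasts will have less power than the pooled one.

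Also:

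- Define pubertal by stage, and restrict the test to patients able to advance. Report those at stage 5 at baseline separately, since they are not restaged.
- Drop the +4 category if the definition makes it impossible, and say how a lower later stage is counted.
- Keep the sex-specific shift tables and all Week 52 results descriptive, with no p-value. Attach no p-value to within-arm tables.

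The cost is a few lines of SAP text and one standard procedure call, with no change to data collection. The sex-specific p-values are lost; the tables still show each sex.
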